7.4 Medical History

Medical history data will be mapped using the Medical Dictionary for Regulatory Activities (MedDRA, version 19.0 to system organ class (SOC), and preferred term (PT). This data will be summarized in a frequency distribution. Subjects may have more than one medical history record per SOC and PT. At each level of subject summarization, a subject will be counted once if he/she reports one or more medical history record at that specific level. Subjects must have a medical history of both DPN – Lower Extremities and Type II Diabetes in order to be eligible for the study. Therefore, these events will not be counted in the medical history frequency distribution table, but a footnote will be added that all subjects had both DPN – Lower Extremities and Type II Diabetes in the safety population. A frequency distribution table will be displayed by the safety treatment arms and all subjects even though the medical history information was collected prior to dispensing study drug.

Additionally, collected data on the CRF will be listed by subject, safety treatment arm, verbatim body system, verbatim medical condition/procedure, onset date, and ongoing status/end date.

7.5Questionnaire/Scale Assessments only at Screening or Baseline

These screening questionnaires/scales will be provided in separate individual subject listings. Details of data summarized in one overall questionnaire/scale assessments only at screening or baseline table will be mentioned in the following subsections.

MPB Biostats

Protocol No.: NYX-2925-2001 Statistical Analysis Plan (SAP)

7.5.1 Masquerading Disorders Tool

The Masquerading Disorders Tool (Analgesic Solutions, Wayland, MA) is a screening instrument to help identify subjects with disorders that masquerade as painful diabetic peripheral neuropathy, such as Morton's neuroma, peripheral vascular disease, Achilles tendonitis, arthritis, and tarsal tunnel syndrome. The screening instrument consists of symptom screening questions, and an in-clinic history and examination to target the nature and etiology of the subject's peripheral pain. The results of this assessment tool are provisional, with the final decision based on the clinical judgment of the investigator.

The Masquerading Disorders Tool (MDT) contains 15 sections, where sections 1-14 are comprised of 1-3 questions with each question having a yes or no response. The overall MDT assessment in section 15 will be included in a frequency distribution table:

- Masquerading Disorder Not Present
- Masquerading Disorder Present
- Masquerading Disorder Present; Painful Diabetic Neuropathy as Dominant Pain

7.5.2 Michigan Neuropathy Screening Instrument

The Michigan Neuropathy Screening Instrument is a 15-item, self-administered questionnaire and a lower extremity examination that includes inspection of vibratory sensation and ankle reflexes. It can be used to assess distal symmetrical peripheral neuropathy in diabetes^[7].

The history portion of the Michigan Neuropathy Screening Instrument answered by the subjects contains 15 questions with each question having a yes or no response. Each yes response has a numeric value of 1 and 0 is assigned to no responses. The History Total Score is the sum of all 15 questions with values ranging from 0 to 15. No missing values will be imputed.

The physical assessment portion of the Michigan Neuropathy Screening Instrument will be completed by a study site health professional and is assessed individually for the right and left feet. Each foot has the following assessment with following numeric scores:

- Appearance of Feet Normal: Yes = 0; No = 1
- Ulceration: Absent = 0: Present = 1
- Ankle Reflexes: Present = 0; Present/Reinforcement = 0.5; Absent = 1
- Vibration Perception at Great Toe: Present = 0; Decreased = 0.5; Absent = 1
- Monofilament: Normal = 0; Reduced = 0.5; Absent = 1

A subscale score is determined for both the right and left feet individually. The subscale scores range from 0 to 5 and no missing values will be imputed. The Physical Assessment Total Score will be the sum of both the right and left subscale scores if they are both calculated. Other details are collected if the appearance of the foot is not normal: deformities; dry skin, callus; infection; fissure; and other specify. That data collected will be presented in subject listings, but is not part of the numeric subscale and total scores.

Both the Michigan Neuropathy Screening Instrument History Total Score and Physical Assessment Total Score will be summarized using descriptive statistics in a table.

7.5.3 American College of Rheumatology Fibromyalgia Criteria

The 2010 American College of Rheumatology Fibromyalgia Criteria is a clinician-administered survey that is used as a diagnostic tool for fibromyalgia. The diagnostic criteria for fibromyalgia are met by the following 3 conditions:

- Widespread Pain Index ≥7 and Symptom Severity Score ≥5, or the Widespread Pain Index is 3 to 6 and the Symptom Severity Score is ≥9;
- Symptoms have been present at a similar level for at least 3 months; and
- Subject does not have a disorder that would otherwise explain the pain [8].

The Widespread Pain Index (WPI) is a score comprised of 19 areas where subjects experienced pain within the last week with a yes or no response for each area. Each individual yes response has a numeric value of 1 and 0 is assigned to each no response. The WPI score will have values ranging from 0 to 19. If any of the individual area responses are missing, the WPI score will not be calculated. Here are the 19 areas that will be assessed:

 Shoulder Girdle, Left; Shoulder Girdle, Right; Upper Arm, Left; Upper Arm, Right; Lower Arm, Left; Lower Arm, Right; Hip (Buttock, Trochanter), Left; Hip (Buttock, Trochanter), Right; Upper Leg, Left; Upper Leg, Right; Lower Leg, Left; Lower Leg, Right; Jaw, Left; Jaw, Right; Chest; Abdomen; Upper Back; Lower Back; and Neck

The Symptom Severity (SS) Score is based on 4 questions with each question having a numeric score ranging from 0 to 3. If all 4 questions are given a numeric score, then the Symptom Severity Score will range from 0 to 12. If any of the individual scores are missing, the Symptom Severity Score will not be calculated.

Both the Widespread Pain Index score and Symptom Severity Score will be summarized using descriptive statistics in a table. Additionally, counts and percentages will be presented for subjects reaching these responses for these categories^[8]:

- Widespread Pain Index ≥7 and Symptom Severity Score ≥5
- Widespread Pain Index is 3 to 6 and Symptom Severity Score ≥9

7.5.4 Bedside Sensory Testing Kit

The Bedside Sensory Testing Kit (Analgesic Solutions, Wayland, MA) is used to assess a subject's sensory profile to allow phenotypic identification of subgroups of subjects with painful diabetic peripheral neuropathy who might respond differently to a given treatment. The kit consists of multiple sensory instruments that are applied to different peripheral anatomic sites to evaluate the following phenomena: extent of damage of low threshold mechanoreceptive small fibers in the feet, dynamic mechanical allodynia, punctate hyperalgesia, high threshold mechanoreceptive function, and cold allodynia.

The Bedside Sensory Testing Kit is comprised of 5 sections and individual tests within each section will be completed by the study site principal investigator (PI) or sub-principal investigator (Sub-I):

- Neuropen® Test Low Threshold Mechanoreceptive Function
 - o 10 locations will be selected with test having a yes or no response.
 - Each "yes" response will be scored as a 1 with the total score being the sum of the 10 location with scores ranging from 0 to 10.

- o This will be summarized using descriptive statistics in a table.
- Foam Brush Test Dynamic Mechanical Allodynia
 - o NRS scoring based on an 11-point numerical rating scale/Likert scale ranging from 0 to 10 will be assessed once for each of these locations:
 - Foot
 - Shin
 - Thigh
 - o These 3 scores will be summarized using descriptive statistics in a table.
- Safety Pin Test Punctate Hyperalgesia
 - o NRS scoring based on an 11-point numerical rating scale/Likert scale ranging from 0 to 10 will be assessed 5 times for each of these locations:
 - Foot
 - Shin
 - Thigh
 - o If at least 3 scores are collected for an area, the mean score will be calculated and rounded off by one number after the decimal point.
 - o These 3 mean scores will be summarized using descriptive statistics in a table.
 - The foot, shin, and thigh locations will also be asked once, "Was the pin sharp?" with a yes or no response. This data will be summarized by counts and percentages for the responses.
- Von Frey Filament Test Temporal Summation
 - o NRS scoring based on an 11-point numerical rating scale/Likert scale ranging from 0 to 10 will be assessed 5 times for each of these locations:
 - Foot
 - Shin
 - Thigh
 - The change between the first and last scores will be calculated for each area (last score first score).
 - This change score will be summarized using descriptive statistics in a table.
- Tuning Fork Test Cold Allodynia
 - NRS scoring based on an 11-point numerical rating scale/Likert scale ranging from 0 to 10 will be assessed once for each of these locations:
 - Foot
 - Shin
 - Thigh
 - These 3 scores will be summarized using descriptive statistics in a table.

8. Study Drug Exposure, Rescue Medication, and Other Medications

8.1 Study Drug Accountability

Subjects will be dispensed blinded study drug according to the randomization schedule at visits Week 0 (Baseline) and Week 2. In the event the subject comes in for an unscheduled visit prior to Week 4, they may be dispensed additional blinded study drug.

The following data will be collected and derived at each start and end to the study drug accountability visit intervals:

Parameter	Origin/Derivation
Capsules Dispensed Amount	CRF
Capsules Returned Amount	CRF
Expected Number of Capsules Taken	Derived: (Date Returned – Date Dispensed + 1) x 2 (where the maximum would be 36 because 36 capsules are issued at each dispensing visit)
Estimated Number of Capsules Taken	Derived: Number of Capsules Dispensed Amount – Number of Capsules Returned Amount
Treatment Compliance (%)	Derived: 100 x Estimated Number of Capsules Taken / Expected Number of Capsules Taken (rounded off by one number after the decimal point)

The Overall Treatment Compliance (%) will be calculated as:

• 100 x \sum (Estimated Number of Capsules Taken at All Visits) $/\sum$ (Expected Number of Capsules Taken at All Visits) and rounded off by one number after the decimal point

A subject will be classified as being compliant with study drug administration if their calculated compliance by analysis visit and overall is between 80% and 125%, inclusive. Descriptive statistics will be summarized for treatment compliance by returning analysis visits Week 2, Week 4, and Overall. The following categorical ranges will be summarized in a table for those same analysis visits and overall:

• <80%, 80-125%, >125%, and Not Reported

Any study drug not returned during a subject's visit where study drug compliance is assessed will assume that all of that study drug was taken by the subject for analysis purposes. No adjustments will be made even if comments are documented on the CRF that stated lost samples were reported by the subjects. All study drug accountability comments will be provided in a subject listing. If a subject does not return study drug after being dispensed study drug, then the study drug returned and overall treatment compliance will be set to missing.

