8 STUDY TREATMENT

8.1 Dosing and Administration

This is a double-blind study. Subjects, study personnel, and the sponsor will be blinded to study treatment.

Subjects will be dispensed blinded investigational product according to the randomization schedule. Investigational product will be dispensed at the Week 0 (Baseline) and Week 2 visits; at each of the 2 visits, subjects will receive a 2-week supply of investigational product. Subjects will be instructed to take 2 capsules of investigational product once daily by mouth.

Randomized treatment will be:

NYX-2925 by mouth once daily for 4 weeks, or

Placebo by mouth once daily for 4 weeks

Subjects will also be dispensed 1 bottle of acetaminophen to be used as rescue medication at the visits identified in Table 3. Rescue medication will consist of 500 mg caplets of acetaminophen. Subjects will be instructed that up to 2 g/day of rescue medication are allowed and should be reported daily via their study-issued handheld device.

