8.2 Investigational Product Description, Appearance, Packaging, and Labeling

NYX-2925 is a small molecule ((2S, 3R)-3-hydroxy-2-((R)-5-isobutyryl-1-oxo-2,5-diazaspiro[3.4]octan-2-yl)butanamide), that will be provided as capsules for oral administration. Matching placebo capsules will also be provided.

The oral formulation of the investigational product comprises inert United States Pharmacopeia (USP)-grade excipients in a capsule made of hydroxyl-propyl cellulose. The content of the capsule is a dry blend of NYX-2925, microcrystalline cellulose, National Formulary (NF), pregelatinized starch, NF, and magnesium stearate USP.

Matching placebo capsules will contain only the inactive ingredients listed previously.

The investigational product will be provided in a blister-pack kit. The labels will include "NYX-2925 Oral Capsules or Placebo to Match", capsule count, kit number, storage conditions, retest date, sponsor name, and investigational use statement. Each kit of investigational product will include 18 capsules (nine 2-capsule rows) of either matching placebo capsules or NYX-2925 capsules according to the randomization schedule. The investigational product will be packaged in a way that each dose will be 2 capsules/row.

The sponsor will provide investigative sites with sufficient amounts of investigational product to conduct the study.

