5.1.1 Day 1/Date of First Dose

Day 1 is also referred to in the protocol and CRF as Visit 2, Baseline Visit, and Week 0.

The date of first dosing of study drug is not collected on the CRF because subjects are given study drug to administer themselves. Therefore, it will be assumed that Day 1 is the same day as the first dosing day of study drug for subjects in the safety population later described in the SAP in Section 6.1.

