6.3 PP Population

The Per Protocol (PP) population will be based on all subjects in the efficacy population and the following criteria:

- Subjects received the same study drug throughout the duration of the study;
- Subjects received the same study drug to which they were randomized;
- Subjects met the randomization inclusion criteria described in Section 7.1 of the protocol;
- Subjects did not use any of the prohibited concomitant medications listed in Section 8.7 of the protocol;
- Subjects who have an overall study drug treatment compliance between 80% and 125%;
- Subjects have an observed mean NRS score assessing average pain intensity in the past 24 hours calculated within the Week 4 efficacy analysis visit window.

Subjects in the PP population will be defined based on a review of the relevant data by the Sponsor prior to database lock. However, subjects dispensed the wrong treatment arm (i.e., a treatment arm other than the one they were randomized to) will be removed from the PP population. Subjects in the PP population will be analyzed based on the planned treatment they were randomized to in the study.

7. Disposition, Baseline, and Other Characteristics

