8.3 Rescue Medication

Subjects will also be dispensed 1 bottle of acetaminophen to be used as rescue medication at visits Screening, Week 0 (Baseline), and Week 2. Each bottle will contain either 100 or 175 caplets and this amount will be collected on the CRF. Rescue medication will consist of 500 mg caplets of acetaminophen. Subjects will be instructed that up to 2 g/day of rescue medication are allowed and should be reported daily via their study issued handheld device.

The following data will be collected and derived at each start and end to the rescue medication accountability visit intervals:

Parameter	Origin/Derivation
Caplets Dispensed Amount	CRF
Caplets Returned Amount	CRF
Estimated Number of Days Taken	Derived: Date Returned – Date Dispensed + 1 (where the maximum would be the number of caplets issued at each dispensing visit)
Estimated Number of Caplets Taken	Derived: Number of Caplets Dispensed Amount – Number of Caplets Returned Amount
Average Rescue Medication Taken (g/day)	Derived: 0.5 x Estimated Number of Caplets Taken / Estimated Number of Days Taken (rounded off by two numbers after the decimal point)

The Overall Post-Baseline Average Rescue Medication Taken (g/day) will be calculated as:

 $0.5 \times \Sigma$ (Estimated Number of Caplets Taken After Dispensed at the Baseline Visit) / Number of Study Days at the Week 4/Early Termination Visit (rounded off by two numbers after the decimal point)

Descriptive statistics will be summarized for average rescue medication taken (g/day) by returning analysis visits Baseline, Week 2, Week 4, and Overall Post-Baseline.

Any rescue medication not returned during a subject's visit where rescue medication accountability is assessed will be set to missing for analysis purposes. If the caplets returned amount was collected as

zero on the CRF and the CRF collected a comment that the rescue medication bottle was not returned, then the caplets returned amount will be set to missing for analysis purposes.

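### SAP 8.1 counts the Week 2 visit day twice in expected capsules (58 instead of 56), and its two sentences on unreturned study drug overlap; Per Protocol status can turn on either at the margins

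*SAP*

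**What the plan says.** **Expected capsules.** SAP 8.1 (Study Drug Accountability) gives the expected number for each interval as "Derived: (Date Returned – Date Dispensed + 1) x 2", with a ceiling: "where the maximum would be 36 because 36 capsules are issued at each dispensing visit". Overall compliance is 100 times the sum of estimated capsules taken, divided by the sum of expected capsules, over all visits. A subject is compliant between 80% and 125% inclusive.

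**Dosing and visits.** Protocol 8.1 states: "Subjects will be instructed to take 2 capsules of investigational product once daily by mouth". SAP 5.1.1 takes the dispensing day as the first dosing day: "it will be assumed that Day 1 is the same day as the first dosing day". Protocol 6.1 and 10.3.1 have the first supply returned and the second dispensed at the same Week 2 visit (Day 14 ± 2). The Week 4 visit is Day 28 ± 2. SAP 8.1 also allows extra dispensing at unscheduled visits.

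**Unreturned study drug.** SAP 8.1 first says that drug not returned at a visit where compliance is assessed is taken to have been used, with no adjustment for reported losses. Later in the same paragraph, for a subject who does not return study drug after it was dispensed, "then the study drug returned and overall treatment compliance will be set to missing".

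**Use of the result.** SAP 6.3 makes this a Per Protocol criterion: "Subjects who have an overall study drug treatment compliance between 80% and 125"%. It does not mention missing compliance.

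**Rescue medication.** SAP 8.3 counts days per interval in the same inclusive way, with its own ceiling ("where the maximum would be the number of caplets issued at each dispensing visit"). Overall post-baseline rescue use is instead divided by the study-day number at Week 4 or early termination.

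**The concern.** Counting both end dates is right for a single interval. It is not right when intervals that share an end date are added together. The Week 2 day enters both intervals, so the denominator of overall compliance is too large and the 80% and 125% limits do not act where they are stated.

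The unreturned-drug sentences raise a separate problem. A subject who attends Week 4 empty-handed fits both. One yields a percentage and the other a missing value, and Per Protocol entry depends on that quantity.

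At stake are the compliance table, the by-interval rescue averages, and membership of the Per Protocol set, which supports five tables including an ANCOVA and an MMRM on average pain.

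**Working it through.** **Inputs.** 2 capsules daily (Protocol 8.1); Day 1 is the first dosing day (SAP 5.1.1); visits on nominal Days 1, 14 and 28 (Schedule of Procedures); formula, ceiling and band from SAP 8.1.

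**The plan's own figure.** Protocol 8.2 says: "Each kit of investigational product will include 18 capsules (nine 2-capsule rows"). Assuming two kits per dispensing visit, 2 × 18 = 36 capsules, or 18 days at 2 per day. The ceiling of 36 reproduces.

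**Expected capsules, nominal days.**
- First interval: (14 − 1 + 1) × 2 = 28.
- Second interval: (28 − 14 + 1) × 2 = 30.
- Sum as written: 58. Each day counted once: 28 × 2 = 56.

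**Full adherence.** 56/58 = 96.6%. If the dose on the final return day is not taken, 54/58 = 93.1%. Both lie well inside the band.

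**Where the band acts.**
- As written: 0.80 × 58 = 46.4 and 1.25 × 58 = 72.5, so 47 to 72 capsules (72 is all that is issued at two visits).
- Day counted once: 0.80 × 56 = 44.8 and 1.25 × 56 = 70, so 45 to 70 capsules.

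| Capsules counted as taken | As written (/58) | Day counted once (/56) |
|---|---|---|
| 45 | 77.6%, out | 80.4%, in |
| 46 | 79.3%, out | 82.1%, in |
| 71 | 122.4%, in | 126.8%, out |
| 72 | 124.1%, in | 128.6%, out |

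No other total changes status. The 72-capsule row is a subject who returns nothing at either visit and is assumed to have taken everything.

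**Visit windows.** Taking Week 2 on Day 12, 14 or 16 and Week 4 on Day 26, 28 or 30, the excess is 2 capsules in every combination but one. With visits on Days 12 and 30 the ceiling cuts the second interval from 38 to 36, and 24 + 36 = 60 = 2 × 30. Where the Week 4 visit is on Day 26, status changes at 42, 43, 66 or 67 capsules. Where it is on Day 30 and the excess remains, it changes at 48 or 49.

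**Unscheduled dispensing.** Intervals of Days 1–7, 7–14 and 14–28 give 14 + 16 + 30 = 60 expected, an excess of 4.

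**Unreturned drug.** With 28 capsules taken in the first interval and nothing returned at Week 4, the assumed-taken sentence gives (28 + 36)/58 = 110.3%, which meets the criterion. The other sentence, if it applies, gives missing. With nothing returned at either visit the results are 124.1% or missing.

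**Rescue.** The Baseline–Week 2 interval has 14 days and the Week 2–Week 4 interval has 15, or 29 in total for 28 study days. If the Week 2 day belongs to the earlier interval, the later average is 14/15 = 0.933 of its value, about 7% low. Visit 2 is likewise shared with the screening interval. The overall post-baseline figure divides by study days and has no double count.

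**The case against.** The strongest reply is that little follows. The excess is 2 capsules, about 3.6% of 56. Fully adherent subjects remain compliant, and the documents do not show that any subject falls on the totals that change. The sponsor reviews Per Protocol membership before database lock. The primary analysis uses the Efficacy Population, whose definition in SAP 6.2 has no compliance criterion. None of the Per Protocol tables is marked for topline. All of this stands and limits the weight of the point. It does not make the denominator right.

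A reader might infer that the two unreturned-drug sentences are flatly opposed. They need not be. The first can be read as a shortfall at an attended visit, the second as a subject who never returns any drug, for whom no return date exists. SAP 8.2 supports this reading: it uses nearly the same condition as a last resort for missing exposure. What remains is that SAP 8.1 does not draw this line, so the empty-handed attender fits both.

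A reader might also make much of an unreturned supply reading 36/28 = 128.6% in the first interval but 36/30 = 120% in the second. That contrast affects only the by-visit compliance summary. SAP 6.3 uses overall compliance, which is 64/58 = 110.3% whichever single supply is unreturned, if 28 capsules are taken in the other interval.

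On rescue, an as-needed bottle is available on both end dates, so the 7% is not a firm bias. It depends on how use is assigned to the shared day.

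**Conclusion.** Two minor defects hold.

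- **Double count.** On nominal days the expected total is 58 instead of 56. Full adherence reads 96.6%, and Per Protocol status changes only at 45, 46, 71 or 72 capsules. The by-interval rescue averages share the double-counted day; overall rescue use does not.
- **Unreturned drug.** For a subject who attends and returns nothing, overall compliance is either a percentage (110.3% or 124.1% in the cases above) or missing, depending on the sentence applied. SAP 6.3 does not say what missing means for entry.

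It would be tempting to conclude that compliance and Per Protocol membership are wrong throughout. The documents do not support that: the double count acts only at the edges of the band, and how many subjects sit there cannot be known from them. Nor is the ceiling of 36 at fault; the source is the added day in the formula beside it. The effect is confined to the compliance and rescue tables and the supportive Per Protocol tables. The primary analysis does not change.

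The figures assume nominal visit days, two kits per dispensing visit and one dose on each of Days 1 to 28. The documents do not say whether a dose is taken on the return day.

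**What to change.** 1. In SAP 8.1, count each shared visit day once. Either drop the added day from every interval after the first, including those that start at an unscheduled dispensing (28 + (28 − 14) × 2 = 56), or make the denominator of overall compliance 2 × the total number of treatment days. The first option also puts the two by-visit figures on the same footing.
2. In SAP 8.3, do the same for the by-interval rescue averages, including the interval that starts at Visit 2. Leave the overall post-baseline figure as it is.
3. In SAP 8.1, state which case each unreturned-drug sentence covers: for example, assumed taken for a shortfall at an attended visit, including one where nothing is brought back, and missing when no drug is ever returned. Keeping the assumed-taken rule for attended visits also leaves intact the wrong-kit deviation check in SAP 8.2, which needs an estimated capsule count above zero.
4. In SAP 6.3, say whether missing overall compliance excludes a subject from the Per Protocol set.

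The cost is a formula change in two sections and two or three sentences, with no new data. It should be settled before the pre-lock review of Per Protocol membership.
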